#### **6.2.1.5 Weeks 7-8**

After completing the 24-hr PKPD study, subjects will be discharged from the research facility and continue on their usual HC oral dosing schedule for 1 week prior to initiation of the SQHC pump. During this time, cortisol, 17OHP, and D4A concentrations will be analyzed to determine that the pump has delivered HC as expected and cortisol, 17OHP, and D4A concentrations are in an acceptable range. SQHC will be recalculated as needed before initiating the pump if cortisol, 17OHP, or D4A concentrations are not generally in a desired range.

#### **6.2.1.6 Week 8**

The nurse coordinator will call the subject/family to review daily blood pressure readings, adverse events, medications and the subject's dairy.

#### **6.2.2 Weeks 9-14 (SQHC Pump)**

### **6.2.2.1 Weeks 9-13**

Week 9 (outpatient visit) The patient will meet [name] and the study nurse coordinator at Nucleus (Prism) for initiating the 6-wk SQHC pump phase. The patient will have a physical exam and the nurse coordinator will review the patient's recorded daily blood pressure, subject diary, adverse events and any medications taken. It is our standard policy to make sure that families have parenteral hydrocortisone to use during emergencies. We will instruct the patients to call [name] before administering any parenteral dose during this phase. After the first four supervised home visits by the nurse coordinator, the family, as instructed will replace the HC infusion syringe and solution, and the site of SQ infusion every 72 hours. As with insulin, we recognize that there may be variability in drug absorption associated with different sites of SQ injection pump infusion therapy. Each subject will be evaluated for appropriate site for SQ infusion (i.e. gluteal area, abdominal area).. Parents will be instructed to visually inspect the parenteral HC solution for particulate matter and discoloration prior to administration into the pump.

After the outpatient visit, during week 9, the subject/family will be called on the days that the RN coordinator is not completing home visits. This call is the review pump use, adverse events and other questions or concerns.

Weeks 9-13: The nurse coordinator will visit subjects at home seven times for safety monitoring, which includes a nursing assessment, and measurement of cortisol, 17OHP, ACTH and D4A concentrations during the SQHC pump period. During the home visits, along with the blood draws, saliva will be collected and measured through VerOFy® cortisol (VCORT) with the remaining salivary sample sent to Quest Diagnostics for free cortisol measurements through LC-MS/MS assay. VCORT is IDE exempt per the requirements outlined in 21CFR812.2(c) and in 21CFR809.10(c). The nurse coordinator will complete their assessment and review the patient's recorded daily blood pressure, subject diary, adverse events and any medications taken. At Visit 13, an Actigraph Link accelerometer will be provided for monitoring daily activity and sleep patterns for one week.

To note, the use of the VerOFy® may be restricted based upon the company's availability to provide the device to our site site. As noted under the secondary/exploratory objectives, the VerOFy® will not be used to "make dosing decisions or diagnoses and formal monitoring will be accomplished using serum cortisol sampling." We therefore will collect and record results only at time of availability for use of the device. The informed consent will notify participants/families that this sampling and measurement will be based upon when the device is available at the time of study visit..

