#### 6-WEEK PUMP TREATMENT

All subcutaneous pump settings of hydrocortisone (timing and dose) can only be set by the researchers. The SQ infusion site will be changed every 3 days. As there may be variability in drug absorption associated with different sites of SQ infusion therapy, Each subject will be evaluated for appropriate site for SQ infusion (i.e. gluteal area, abdominal area) to ensure proper placement. A clinician will establish contact every day for the first week via telephone. All patients will be seen at home twice each week during the first and second week at the time of injection site changes and once a week thereafter while on the pump to evaluate proficiency in changing the injection site; to collect blood for cortisol, 17OHP, ACTH, and D4A concentrations; and to inspect the injection site integrity.

*Dose Adjustments During Pump Therapy.* During the 6-week pump treatment, multiple cortisol, D4A, ACTH and 17OHP concentrations will become available and they may suggest, along with clinical impressions, that the pump dosing setting needs to be revised. It is critical to note that subjects will not be required to stay on the initial dosing schedule for 6 weeks. Rather, standard clinical practice will be used to guide SQHC pump dosing adjustments. Specifically, D4A and 17OHP concentrations will be evaluated along with clinical information provided by the patient that are indicative of hypocortisolism such as fatigue, nausea, diaphoresis, low blood pressure, dizziness or headache. This is currently the standard of care for pediatric CAH patients. Should incongruous information be observed, clinical impressions take precedence along with D4A concentrations, and then 17OHP concentration. Cortisol concentrations are not generally part of routine patient care and will play a lesser role in dosing changes. The changes in dose settings may involve increasing or decreasing the HC TDD, or perhaps changing the percentage of TDD administered at a given time, but the 3-hr dosing intervals will remain fixed.

A 24-hr PKPD study will be performed during admission 3 (week 14) using the same sampling schedule as admission 2.

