#### **6.2.1.4 Week 7 (SQHC Pump 33 hours)**

At week 7, subjects will be re-admitted for Crono P subcutaneous HC (SQHC) infusion pump training in which the device will be used for 33 hrs and include a 24-hr PKPD study while on the SQHC pump. Training will emphasize proper aseptic catheter placement, care of the insertion site, reconstituting the solution and filling the infusion syringe. HC sodium succinate (SOLU-CORTEF) sterile powder will be used for the SQHC pump as it is FDA approved for intramuscular and intravenous routes for CAH and Addison's disease. HC sodium succinate comes in a two-compartment vial (Act-O-Vial) containing a 100 mg dose in the lower compartment and 2 ml sterile water in the upper compartment (100 mg/2 ml). Parents will be instructed to further dilute the solution with another 8 ml of 0.9% normal saline into the infusion syringe, for a final concentration of 100 mg/10 ml (10 mg/ml). Parents will be trained to visually inspect the HC sodium succinate solution for particulate matter and discoloration. The parents of the children seen at the CAH Center are already familiar with the 100 mg Act-O-Vial as the IM HC sodium succinate injection is used at home in cases of acute stress or illness when the children are not able to take oral medication.

Subjects will have a physical exam. Pump therapy during this admission will begin at 9 pm and continue for 33 hours. We will use each patient's total daily dose (TDD) of HC to determine the doses to be delivered during the 33-hr period. The 24-hr schedule and percentage of the TDD of HC will be as follows: approximately 60% of the TDD of HC will be delivered in 3 equal pulses at 0300, 0600 and 0900. Another 35% will be delivered in 3 equal pulses at 1200, 1500 and 1800 and the remaining 5% at 2100 and 2400. Following delivery of the 9:00 pm, 12:00 am, and 3:00 am pulses, a 24-hr PKPD study will be initiated at the 6:00 am pulse using the same sampling schedule of cortisol, 17OHP, ACTH and D4A as the first admission. Urine collection will proceed as the first admission beginning at 0600. Saliva samples will be collected at the same time points as in admission 1 (0600, 0700, 1200, 1300, 1800, and 1900) irrespective of dosing. Salivary samples will be sent to Quest Diagnostics for adrenal steroid measurements through LC-MS/MS assay.

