### **7.1.3 Dosage adjustments**

The following dosage adjustments may be made during the course of the study in the event of intercurrent illness, pump failure or symptoms of adrenal insufficiency occur.

- For fever > 101 degrees F: add oral hydrocortisone to the patient's regimen, which will be double the amount of the daily dose that the patient receives through the SQ pump. The additional oral stress hydrocortisone dose will be divided in 4 equal doses every 6 hours. The subject's family will be instructed to administer an antipyretic (Tylenol, ibuprofen, etc).
- For a serious physical injury or broken bone(s), administer a stress dose of hydrocortisone as described above.
- In the event of severe illness, trauma, or inability to tolerate oral hydrocortisone, unconsciousness, or repeated vomiting: 75 mg/m^2/day of Solucortef intramuscular injection will be administered immediately. The family will be instructed to seek Emergency Department care to initiate IV hydrocortisone and fluid replacement as they typically do as part of the standard therapy to prevent adrenal crisis.
- In the event of pump failure, patients will be instructed to resume their usual oral hydrocortisone dose until a replacement pump is given to the family.
- In the event of an occlusion that results in missed hydrocortisone dosing, patients will be instructed to change the infusion set and notify the investigators. If occlusion persists, patients will be instructed to resume their usual oral hydrocortisone dose until occlusion is resolved.
- A pump malfunction that results in delivery of the entire reservoir (worst case scenario 100 mg of hydrocortisone) is not a life threatening event as children receive similar or greater amounts of hydrocortisone during illness. If the entire reservoir is delivered, patients will be instructed to notify the investigators and return to their usual oral hydrocortisone dosing until a replacement pump is given to the family.

At all times the PI will be available to the families. If pump therapy is stopped at any point the investigator will evaluate the participant and re-initiate the pump treatment when deemed clinically appropriate. Once the pump is resumed, pump treatment will be continued in order to meet the total 6 weeks of pump treatment.

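### Section 6.2.2.1 tells families to call before any parenteral dose in the pump phase, with no exception for the emergencies in which Section 7.1.3 requires an immediate injection; the two conflict if the call delays the dose or goes unanswered

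*Combined protocol and SAP*

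**What the plan says.** Section 6.2.2.1 describes the start of the six-week ambulatory pump phase. It says "It is our standard policy to make sure that families have parenteral hydrocortisone to use during emergencies". The next sentence says that patients will be told to call a study contact, whose name is redacted in the public text, "before administering any parenteral dose during this phase". No emergency is exempted.

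Section 7.1.3 covers dose changes for illness, pump failure and symptoms of adrenal insufficiency over the course of the study, so it includes the pump phase. For five emergencies (severe illness, trauma, oral hydrocortisone not tolerated, unconsciousness, repeated vomiting) it says that a Solu-Cortef "intramuscular injection will be administered immediately". The family is then to go to the Emergency Department "as they typically do as part of the standard therapy to prevent adrenal crisis". No call is mentioned in that item. The section ends with the assurance "At all times the PI will be available to the families", and Section 9.3 adds that the investigator can be paged at any hour.

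Two background statements matter. Section 6.2.1.4 notes that the intramuscular "injection is used at home in cases of acute stress or illness when the children are not able to take oral medication", so families already know the technique. Section 4, under the six-week pump treatment, says "All subcutaneous pump settings of hydrocortisone (timing and dose) can only be set by the researchers".

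**The concern.** The call-first sentence is unqualified and follows directly on a sentence about emergency stock. Its natural subject is therefore the rescue injection. It is also limited to the pump phase, so it reads as a study rule added on top of what families normally do. Taken literally, it puts a telephone call ahead of a dose that Section 7.1.3 wants given at once.

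What is at stake is a delayed rescue dose. A family cannot raise the pump dose, because only the researchers can change the settings. If the child cannot take or keep down oral hydrocortisone, the injection is the only increase the family can give at home. Section 9.3 foresees pump failures that raise no alarm, and the fallback for pump failure in Section 7.1.3 is the usual oral dose, which does not help a child who is vomiting. Section 2 reports a median half-life of 58 minutes for hydrocortisone in these children, with most of a dose gone within 4-5 hours, so time matters. A parent alone with an unconscious child should not have to decide which of two study instructions comes first.

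**Working it through.** No arithmetic applies; the check is a comparison of texts.

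| Question | Section 6.2.2.1 | Section 7.1.3, emergency item |
|---|---|---|
| When does it apply? | Six-week pump phase | Whole study, so also the pump phase |
| Which doses? | Any parenteral dose | Intramuscular hydrocortisone in five listed emergencies |
| What comes first? | A call to the study contact | The injection, at once |
| Emergency exception? | None stated | Not applicable |
| Refers to the other section? | No | No |

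**Do they overlap?** Yes. An intramuscular injection is a parenteral dose, and each of the five emergencies can arise during the pump phase. The call-first sentence cannot sensibly refer to pump pulses. These are preset at three-hour intervals by the researchers, and a call before each would make no sense.

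**Does another section settle the order?**
- Section 9.3 tells families to contact the investigator straight away for signs of adrenal insufficiency. It does not place that contact before or after an injection.
- Section 10.4 mentions the emergency protocol that is part of standard care, but the sentence concerns oral stress doses taken in addition to the pump.
- Other mentions of home injection, such as those in Sections 6.2.1.4 and 7.1.2, describe what parents already know. They set no rule for this phase.

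**Three situations follow.**
1. The call is answered at once. The family can call and inject within moments, and both sections are satisfied.
2. The call would take time. Following 6.2.2.1 delays the injection; following 7.1.3 breaks the call-first rule.
3. The call is not answered. The conflict is the same, and no text says what to do about an unanswered call.

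The inconsistency is therefore confined to the second and third situations.

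**Can the delay be sized?** No. The documents give no expected rate of adrenal crisis, no response time for the contact, and no figure from which either could be derived.

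**The case against.** The case for leaving the text alone is a fair one. Section 7.1.3 is the specific section for intercurrent illness, and an instruction to inject at once is itself an instruction not to wait. Its items on occlusion and on accidental delivery of the whole reservoir ask families to notify the investigators; its emergency item asks for no call. That contrast supports injecting first. Families are practised in home injection, the Emergency Department step is tied to their usual care, and the investigator is reachable at all hours. Week 9 also has daily contact by visit or telephone.

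Most of this stands, and it makes inject-first the sensible reading. It does not remove the problem. Availability makes a call feasible without waiving it, and familiarity with usual care does not cancel a rule written for this phase.

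Two details of 7.1.3 could be pressed: its opening is permissive about adjustments, and it does not name who injects. But the emergency item itself is mandatory, and sending the family to the Emergency Department afterwards implies an injection at home.

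A reader might go further and infer that the protocol forbids an emergency injection without permission, or that its two sections cannot both be obeyed. The text does not support either. Section 6.2.2.1 asks for a call, not for approval, and a prompt answer satisfies both sections. Nor do the documents show that families were in fact told to wait. Consent pages were removed before publication, the emergency protocol mentioned in Section 10.4 is not reproduced, and no family handout is included. That the redacted contact is the investigator who carries the pager is plausible but not shown.

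**Conclusion.** The point holds as a limited inconsistency in a safety instruction. Section 6.2.2.1 requires a call before any parenteral dose in the pump phase, Section 7.1.3 requires an immediate injection in five emergencies, and no visible text says which prevails when the call would delay the dose or is not answered. This is more than missing detail, because a stated rule, followed to the letter, could hold up a rescue dose.

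Its size cannot be given as a number. A reader might try to express the shortfall through the fever rule, under which oral hydrocortisone is added, "which will be double the amount of the daily dose that the patient receives through the SQ pump". That is an oral regimen for a different trigger. The dose at issue is an intramuscular one, stated as 75 mg/m²/day, so a comparison of pump and fever doses does not measure the effect of a late injection.

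The conclusion rests on the protocol wording alone, and on two readings: that the call-first sentence covers the emergency stock named just before it, and that the family gives the injection at home. Practice at the site may already be safe. Sample size, endpoints and analysis are untouched.

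**What to change.** Amend the call-first sentence in Section 6.2.2.1, for example:

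> In the pump phase, families will call the study contact before giving a parenteral dose, except in the emergencies listed in Section 7.1.3. In those they inject immediately, seek Emergency Department care, and then call.

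Call-first stays for every other parenteral dose, so oversight of non-emergency dosing is kept. Repeating the sentence in Section 9.3 is optional. Any written instructions given to families should carry the same wording.

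The cost is a short protocol amendment. The only downside is that the investigator learns of an emergency injection after it has been given. Visits, sample size and analysis do not change.

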### **6.2.2.2 Week 14 + 5 days**

At week 14 + 5days, subjects will be admitted for a final SQHC pump 24-hr PKPD study. A physical exam will be performed. This study will occur at the 6:00 am pulse using the same sampling schedule of cortisol, 17OHP, ACTH and D4A as the previous two admissions. Urine collection will proceed as the first admission. Saliva samples will be collected at the same time points as in admission 1 and 2. Salivary samples will be sent to Quest Diagnostics for adrenal steroid measurements through LC-MS/MS assay. QoL, sleep and mood surveys and NIH toolbox cognitive domain measures will be repeated. Once the PKPD study is complete, subject will discontinue use of the pump and resume their usual oral HC regimen. The subject's diary, adverse events and medications taken will be reviewed. The Actigraph will be returned.

## 6.2.3 Weeks 15 (+ 1 day)-20 (Oral HC follow-up)

### 6.2.3.1 Week 15 (+ 1 day)-18

We will continue to follow subjects with weekly phone calls while they are on their usual oral HC dose regimen. The coordinator will discuss any adverse events and medications taken, along with reviewing the subject's diary.

### 6.2.3.2 Week 19

The nurse coordinator will visit the subject at home. The will include a nurse coordinator assessment that includes reviewing the patient's diary, adverse events and medications taken. An Actigraph Link accelerometer will be provided and used to monitor daily activity and sleep patterns for one week. These will be monitored by study personnel.

### 6.2.3.3 Week 20

Outpatient visit. Subjects will have a physical exam. Quality of life questionnaire, sleep and mood surveys and NIH toolbox cognitive domain measures administered. Patient's diary will be reviewed and collected by the study staff. Adverse events and medications will be reviewed.

Schedule of Events																			
Week	0	1	6	7	8	9	9 #1	9 #2	10 #1	10 #2	11	12	13	14 + 5 Days	15+1 Day - 18	19	20	Unscheduled Visit f	
Med	Oral HC				SQHC (1day)		Oral HC		Home SQHC Pump						Oral HC				
Visit Type	Outpatient (UMMC)	Overnight	Home	Overnight	Phone	Outpatient (PfRISM)	Home	Home	Home	Home	Home	Home	Home	Home	Overnight	Phone	Home	Outpatient (PfRISM)	Home/ Outpatient
Consent	X																		
Eligibility	X																		
Medical History	X																		
MD Exam	X	X		X		X									X		X	X	
Tanner Staging	X																X		
RN Assessment			X				X	X	X	X	X	X	X	X	X	X		X	
Pump/Syringe Education				X		X	X	X	X	X								X	
QoL, Mood, Sleep Surveys	X														X		X		
Cognitive Tests	X														X		X		
Actigraphy a			X												X		X		
PKPD sampling b	X		X												X				
24hr urine collection c	X		X												X				
Cortisol, 17OHP, D4A, ACTH							X	X	X	X	X	X	X	X				X	
VerOfy cortisol (saliva)							X	X	X	X	X	X	X	X				X	
Saliva (to Quest)	X		X				X	X	X	X	X	X	X	X				X	
Daily BP				X	X	X	X	X	X	X	X	X	X	X				X	
Subject Diary	X	X	X	X	X	X	X	X	X	X	X	X	X	X	X	X	X	X	
Adverse Events	X	X	X	X	X	X	X	X	X	X	X	X	X	X	X	X	X	X	
Con Meds	X	X	X	X	X	X	X	X	X	X	X	X	X	X	X	X	X	X	
Phone Call					X	X d									X e				
NOTES:																			
a Actigraph to be provided at visit for use for 7 days, returning at next visit																			
b PKPD: samples to Quest for cortisol (free & total), ACTH plasma, 17-OHP, D4A, & ACTH at all timepoints																			
c Urine collection of 20 mL q12h, store frozen at -80C																			
d Phone call will occur daily during week 9 (except for outpatient & home visit days)																			
e Phone call will occur once a week for weeks 15 through 18																			
f any of the study activities noted below may be performed per investigator discretion																			

Version 10 SEPT 2019

\* Schedule of events will follow as described above with a time window of +/- 1 day for completion of study visits

### **6.2.4 Subject Withdrawal**

Subjects may be taken off the study by the Principal Investigator for the following reasons:

- Safety reasons
- Failure to adhere to the protocol requirements
- Subject withdraws consent
- The study terminates early.

Subjects will be instructed not to stop taking the cortisol if they withdraw from the study. Subjects receiving SQHC pump therapy will be asked to return to the clinic for pump removal and to resume taking oral steroids. If subjects are willing, we will ask them to complete the follow up visit at the time they withdraw from study to capture any final data.

## **7 Study Drug**

[figure not shown]
### **7.1 Solu-Cortef® (hydrocortisone sodium succinate for injection)**

#### **7.1.1 Description**

SOLU-CORTEF Sterile Powder is an anti-inflammatory glucocorticoid, which contains hydrocortisone sodium succinate as the active ingredient. SOLU-CORTEF Sterile Powder is available in several packages for intravenous or intramuscular administration. Our patients use the single-dose 100 mg ACT-O-VIAL that reconstitutes the hydrocortisone powder to provide a final concentration of 100mg/2 mL .

